5.1.4 Surgical variables and complications

The main outcomes of interest are present in below to evaluate the local therapy (RP) of primary tumour. ^[22]

- Operative Duration is defined as the time (mins) from incision to finishing suturing.
- Intraoperative Estimated Blood Loss will be calculate using haematocrit parameters collected during the operation
- Duration of Indwelling Catheterization (Days) is defined as days from the start of surgery to removal of catheter. Institution/hospital local Urinary Catheter Indwelling and/or Removal Protocol will be applicable for each individual site.
- Complications. Percentage of subjects who experience complications and percentage of complication needing intervention in subjects who receive RP will be calculated.
- Urine function will be measured by dichotomous outcomes (continence or incontinence), where outcomes are defined as primarily the use of pads or absence of leakage. Time to Continence (Days) and urinary continence rate at 12 weeks after surgery will be reported.
- Erectile function will be measured by dichotomous outcomes (potent or impotent). Outcome results will be primarily determined by a single question will ask patients if they experience erections sufficiently firm for sexual intercourse. Potent rates in erectile function at 12 weeks after surgery will be calculated.

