8.4.2 Secondary endpoints

• The mean PSA at the end of NHT and PSA change from baseline

- Percentage of positive surgical margins for primary tumour
- Incidence rate of seminal vesicle invasion and involvement rate of pelvic lymph nodes
- Pathological downstaging rate
- Rate of post-surgical PSA decreased to less than 0.1ng/ml

Surgical-related variables and complications Operative Duration is defined as the time (mins) from incision to finishing suturing.

Intraoperative Estimated Blood Loss will be calculate using haematocrit parameters collected during the operation and measured as a continuous variable.

Duration of Indwelling Catheterization (Days) is defined as days from the start of surgery to removal of catheter.

Complications will be presented as the percentage of subjects who receive RP and experience complications and percentage of subjects for complication needing intervention will be calculated.

Urine function will be measured by dichotomous outcomes (continence or incontinence), which outcomes are defined as primarily the use of pads or absence of leakage. Time to Continence (Days) and urinary continence rate at 12 weeks after surgery will be reported.

Erectile function will be measured by dichotomous outcomes (potent or impotent). Outcome results will be primarily determined by a single question will ask patients if they experience erections sufficiently firm for sexual intercourse. Potent rates in erectile function at 12 weeks after surgery will be calculated.

• AEs

Definition and reporting of AEs is referred to Section 6. AEs will be coded using Medical Dictionary for Regulatory Activities (MedDRA). Summary for AEs will be presented by System Organ Class (SOC) and Preferred Term (PT).

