- o Intraoperative Estimated Blood Loss will be estimated using haematocrit parameters collected during the RP surgery where results will be recorded in mL.
- o Duration of Indwelling Catheterization (Days) is defined as days from the start of surgery to removal of catheter

- Complications will be coded using Medical Dictionary for Regulatory Activities (MedDRA Version 23.0 or later). Where results will be summarized as the percentage of subjects who experience complications and percentage of subjects with complications needing intervention, based on RP analysis set.
- Our Urine function will be measured by dichotomous outcomes (continence or incontinence), which incontinence is primarily defined as the use of pads or absence of leakage. Time to Continence (Days) and urinary continence rate at 12 weeks after surgery will be reported. Time to Continence (Days) is defined as days from surgery to the earliest recorded date of continence during post-surgical follow-up period. Subjects who remained incontinence or with missing urine function records at the time of analysis will be censored at his latest visit day with non-missing urine function record. Subjects with no post-surgery records will be censored at day 1. While for continence rate at 12 weeks, missingness will summarized as a separate category.
- Erectile function will be measured by dichotomous outcomes (potent or impotent). Potent or not will be primarily determined by a single question raised by investigator at week 12 visit after RP surgery on whether the patient has experienced erections sufficiently firm for sexual intercourse. Potent rate is defined as the proportion of the subjects who are assessed as potent out of all RP analysis set subjects.
- AEs will be coded using Medical Dictionary for Regulatory Activities (MedDRA V23.0 or above). Summary for AEs will be presented by System Organ Class (SOC) and Preferred Term (PT), where details of analysis will be described in next section.

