4.3.7.3 Urine Function and Erectile function

- Urinary rate and erectile rate at 12 weeks after surgery will be calculated with 95% confidence interval provided. Denominator will be based on RPAS where percentage of subjects with missing records will be reported as a separate category.
- Time to continence (in Days) will be summarized as continuous variable. Median time to continence will be estimated using Kaplan-Meier method and a Kaplan-Meier plot might be

provided as applicable. Subjects who remained incontinence or with missing urine function records will be censored at his latest visit day with non-missing urine function record. Subjects with no post-surgery records will be censored at day 1.

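### SAP 3.2 counts absence of leakage as incontinence: applied literally, this would invalidate the 12-week continence rate and time to continence

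*SAP*

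**What the plan says.** Protocol 2.2 lists time to continence and the urinary continence rate at 12 weeks among the secondary outcome measures. Protocol 5.1.4 calls urine function dichotomous, "where outcomes are defined as primarily the use of pads or absence of leakage". Protocol 8.4.2 repeats this almost word for word: "which outcomes are defined as primarily the use of pads or absence of leakage". Neither sentence says which criterion belongs to which category.

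SAP 3.2 keeps the phrase but attaches it to one category: "which incontinence is primarily defined as the use of pads or absence of leakage". It then builds the time endpoint on the classification: "Time to Continence (Days) is defined as days from surgery to the earliest recorded date of continence during post-surgical follow-up period".

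SAP 4.3.7.3 uses the classification without restating it. For the rate: "Urinary rate and erectile rate at 12 weeks after surgery will be calculated with 95% confidence interval provided". For the time endpoint it gives two summaries: "Time to continence (in Days) will be summarized as continuous variable" and "Median time to continence will be estimated using Kaplan-Meier method". On censoring: "Subjects who remained incontinence or with missing urine function records will be censored at his latest visit day with non-missing urine function record". Operated patients with no post-surgery record are censored at day 1. SAP section 6 declares no change of analysis from the protocol.

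**The concern.** The SAP sentence is the rule that decides who counts as continent, and half of it points the wrong way. It feeds three things: the numerator of the 12-week rate, the event in time to continence, and the decision to censor a patient as still incontinent. Elsewhere the documents only repeat the ambiguous protocol wording, so a programmer or site following the text has nothing to correct it with. If it is followed, the endpoints stop measuring recovery of continence.

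A smaller problem lies in SAP 4.3.7.3. A variable with censored values is to be summarised as if every value were observed, alongside a Kaplan-Meier median that does treat the censoring.

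**Working it through.** The plan gives no numerical figure for continence, so there is nothing to reproduce. The check is logical, followed by an illustration.

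**Step 1: the literal rule by patient state.** The table compares the SAP text with two plausible intentions. One is that presence of leakage was meant. The other is that two statements were merged: pads mean incontinent, no leakage means continent.

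| State | SAP 3.2 as written | If presence of leakage was meant | If two statements were merged |
|---|---|---|---|
| No pad, no leakage | Incontinent | Continent | Continent |
| Pad, leakage | Incontinent | Incontinent | Incontinent |
| Pad, no leakage | Incontinent | Incontinent | Meets both, contradictory |
| No pad, leakage | Continent (meets neither criterion) | Incontinent | Meets neither, unclassified |

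As written, the only patients counted as continent are those who leak without a pad. Both pad-free states are classified the wrong way round. The two plausible intentions agree on the first two rows and part on the last two, so the intended rule cannot be recovered with certainty from the text.

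**Step 2: size of the effect on the 12-week rate (illustration).** Inputs:
- Operated patients: 104 × 0.90 = 93.6, about 94, using the planned number and rate in SAP 1.3.
- Shares of patients in each state: assumed, not in the documents.
- No missing records; pad users count as incontinent.
- 95% intervals by Clopper-Pearson, the method that Protocol 8.5.1 names for the primary endpoint.

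Formulas: intended rate = (no pad and dry)/94; literal rate = (no pad and leaking)/94, with counts rounded to whole patients.

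| Dry and pad-free | Leaking without pad | Intended rate | Literal SAP rate |
|---|---|---|---|
| 50% | 5% | 47/94 = 50.0% | 5/94 = 5.3% |
| 60% | 5% | 56/94 = 59.6% (49.0 to 69.6) | 5/94 = 5.3% (1.7 to 12.0) |
| 70% | 5% | 66/94 = 70.2% | 5/94 = 5.3% |
| 80% | 5% | 75/94 = 79.8% | 5/94 = 5.3% |
| 60% | 0% | 56/94 = 59.6% | 0/94 = 0% |
| 60% | 10% | 56/94 = 59.6% | 9/94 = 9.6% |

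The literal rate does not move with the dry share at all.

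**Step 3: time to continence.** Under the literal rule, a patient who goes from pads to dry never has the event and is censored at the last recorded visit. With so few events, the Kaplan-Meier median would probably not be reached.

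**Step 4: the continuous summary.** A censored time is only a lower bound. Take three hypothetical patients, at the nominal visit days: one first recorded continent at day 30, one at day 90, and one with no record, censored at day 1. Pooling gives (30 + 90 + 1)/3 = 40.3 days; the events alone give (30 + 90)/2 = 60 days. The day-1 value says nothing about recovery yet lowers the pooled mean by about 20 days. An events-only mean leaves out everyone still incontinent. Kaplan-Meier handles both groups.

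**The case against.** The strongest reply is that this is a slip that would be unlikely to be programmed. SAP 3.2 describes a two-category outcome. If sites record continent or incontinent directly, the faulty phrase need not touch the data. That stands: the eCRF is not available here, and a reader who infers that dry patients are in fact being coded incontinent goes further than the documents allow. It does not excuse the text, because no other section gives sites a usable common definition.

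A reader might also infer that continence is observed only at 30 and 90 days after surgery, so that a patient dry from day 31 is recorded about two months late and an interval-censored estimate is required. The documents do not establish this. The schedule in Protocol 4.1 has no row for urine function, there is also a completion/discontinuation visit, and the SAP's wording is compatible with a recorded date of becoming continent. Even if only visit status is held, Kaplan-Meier and an interval-censored estimate agree at the two visits when both are attended. They differ between visits or when visits are missed.

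On the continuous summary, the reply is that Kaplan-Meier is already planned and the SAP does not say that censored times enter the mean. Both are true, so the planned median is not undermined. But neither version of the mean is sound. Nor is the net direction of error known: dating events by visit lengthens times, while averaging censored times shortens them.

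Finally, the documents do not settle how to class a pad user who stays dry. Any particular rule is a choice for the sponsor.

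**Conclusion.** The definition in SAP 3.2 is wrong as written, and nothing else in the documents repairs it. Applied literally, it would invalidate both continence endpoints: in the illustration, 5.3% continent in place of 50.0% to 79.8%. Those figures rest on assumed shares and on literal application. They are not a forecast of the reported result.

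The inversion itself needs no assumption. Whether it reaches the data depends on how the eCRF captures continence and how the derivation is programmed. The effect is confined to secondary endpoints; the primary endpoint and sample size are untouched. The continuous summary of time to continence is a separate, smaller fault. The case for interval censoring is conditional on the eCRF and is not a required change.

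**What to change.** - **SAP 3.2:** replace the definition so that absence of leakage counts toward continence, with one rule that places every combination of pad use and leakage in one category. For example: continence is no pad use and no leakage; incontinence is pad use or any leakage. The sponsor may choose another rule for the dry pad user, but must state it.
- **eCRF:** compare the rule with the question sites actually answer, before database lock.
- **SAP 4.3.7.3:** report time to continence by Kaplan-Meier only and drop the continuous-variable summary.
- **Event dates:** if the eCRF holds only status at visits, say that event times are visit dates. An interval-censored estimate is then optional.
- **Protocol 5.1.4 and 8.4.2:** align the wording at the next amendment. Protocol 10.5 requires ethics committee approval of amendments, so a separate one for this point is not warranted.

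The cost is a few sentences in the SAP, which Protocol 8.1 allows to be amended before data lock, one summary removed from a table, and one check of the eCRF.

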3.3 EXPLORATORY ENDPOINTS

• Incidence of homologous recombination repair mutation in tumor tissue Below 15 homologous recombination repair related genes will be tested for all subjects in RP analysis set:BRCA1, BRCA2, ATM, PALB2, CDK12, RAD54L, RAD51B, RAD51C, RAD51D, FANCL, CHEK1, CHEK2, PPP2R2A, BRIP1 and BARD1.

Among which percentage of subjects with harmful germline and tumor tissue mutation will be summarized based on RP analysis set, and specific percentage for each specific mutation will be summarized as well.

3.4 OTHER ENDPOINTS

• Laboratory safety assessments (Hematology, Chemistry, Urinalysis)

Blood and urine samples for determination of clinical chemistry, hematology, and urinalysis will be taken at the timepoints as indicated in the Study Plan.

The clinical chemistry, haematology and urinalysis assessments will be performed at a local laboratory at the Investigate site. Sample tubes and volume may vary depending on laboratory method used and routine practice at each site.

The following laboratory variables will be assessed:

Table 1 Laboratory Safety Variables

Haematology/Haemostasis (whole blood)	Clinical Chemistry (serum or plasma)
B-Haemoglobin (Hb)	S/P-Creatinine
B-Leukocyte count	S/P-Bilirubin, total
B-Leukocyte differential count (absolute count)	S/P-Alkaline phosphatase (ALP)
B-Platelet count	S/P-Aspartate transaminase (AST)
	S/P-Alanine transaminase (ALT)
Urinalysis (dipstick)	S/P-Albumin
U-Hb/Erythrocytes/Blood	S/P-Potassium
U-Protein/Albumin	S/P-Calcium, total
U-Glucose	S/P-Sodium
	S/P-Creatine kinase (CK)

The Investigator should make an assessment of the available results with regard to clinically relevant abnormalities. The laboratory results should be signed and dated and retained at centre as source data for laboratory variables.

• Eastern Cooperative Oncology Group (ECOG)

Eastern Cooperative Oncology Group (ECOG) performance status scale will be used to evaluate the subject's general well-being and activities of daily life at visit as specified in the schedule, and the scale will be assessed by the investigator following below criteria:.

Grade 0: Fully active, able to carry on all pre-disease performance without restriction.

Grade 1: Restricted in physically strenuous activity but ambulatory and able to carry out work of a light or sedentary nature, e.g., light housework or office work

Grade 2: Ambulatory and capable of all self-care but unable to carry out any work activities. Up and about >50% of waking hours

Grade 3: Capable of only limited self-care, confined to a bed or chair >50% of waking hours

Grade 4: Completely disabled. Cannot carry on any self-care. Totally confined to bed or chair

Grade 5: Dead

• Study Medication Compliance Rate

Compliance with study medication—based on the drug accountability data—will be calculated as the number of implants or tablets taken (dispensed counts – returned counts) divided by the prescribed number of implants or tablets expressed as a percentage. Compliance to study medication (Zoladex or Casodex) will be calculated as follows:

 $\frac{\text{actual implants or tablets taken}}{\text{expected implants or tablets taken}} x \ 100\%$

For subjects who permanently stop the study medication, the number of expected implants or tablets taken will be counted by the date of study withdrawal.

Above analyses will be performed based on FAS..

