3.7.2 Withdrawal of the informed consent

Subjects are free to withdraw from the study at any time (investigational product and assessments), without prejudice to further treatment. A subject who withdraws consent will always be asked about the reason(s) and the presence of any AE. If a subject withdraws from participation in the study, then his/her enrolment code cannot be reused. Withdrawn subjects will not be replaced.

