3.7.4 Completion of the study

For subjects who received RP, it will be considered as completion of the study if the subjects completed the 3 months post-surgical follow-up period. If the subjects who actually can not receive radical prostatectomy within 30 days after 24 weeks neoadjuvant therapy, it will be considered as completion of the study and reason for failure to operate will be collected.

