6.10 Management of IP related toxicities

Laboratory abnormalities including elevated AST, ALT, bilirubin, BUN (blood urea nitrogen), and creatinine and decreased hemoglobin and white cell count have been reported in both Casodex-LHRH analogue treated and flutamide-LHRH analogue treated subjects.

Rare cases of death or hospitalization due to severe liver injury have been reported postmarketing in association with the use of Casodex. Hepatotoxicity in these reports generally occurred within the first three to four months of treatment. Hepatitis or marked increases in liver enzymes leading to drug discontinuation occurred in approximately 1% of Casodex patients in controlled clinical trials.

Serum transaminase levels should be measured prior to starting treatment with Casodex, at regular intervals for the first four months of treatment, and periodically thereafter. If clinical symptoms or signs suggestive of liver dysfunction occur (e.g., nausea, vomiting, abdominal pain, fatigue, anorexia, "flu-like" symptoms, dark urine, jaundice, or right upper quadrant tenderness), the serum transaminases, in particular the serum ALT, should be measured immediately. If at any time a subject has jaundice, or their ALT rises above two times the upper limit of normal, Casodex should be immediately discontinued with close follow-up of liver function.

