8.3 Definitions of analysis sets

Full analysis set (FAS)

The FAS will include all subjects who received at least one dose of study treatment, irrespective of whether some of these subjects may have discontinued treatment prior to the trial's end.

RP analysis set (**RPAS**)

The RPAS is defined as a subset of FAS, which includes all FAS subjects who actually received RP within 30 days by the end of NHT, regardless of prematurely discontinued treatment.

All RP related assessments will be conducted based on RPAS except for the primary analysis, where the denominator will be number of subjects in FAS.

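### For subjects who stop study drug early, SAP 3.4 counts expected doses up to study withdrawal, which understates compliance whenever withdrawal comes after the drug was stopped

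*SAP*

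**What the plan says.** SAP 3.4 (Study Medication Compliance Rate) takes doses used from drug accountability, as dispensed minus returned, and has them "divided by the prescribed number of implants or tablets expressed as a percentage". It then adds a special rule. The rule is triggered by stopping drug ("For subjects who permanently stop the study medication"), but the cut-off it sets is leaving the study: "the number of expected implants or tablets taken will be counted by the date of study withdrawal". The summary is on the full analysis set, so early stoppers are in it. SAP 4.3.5.2 repeats the ratio of actual to expected doses and adds nothing on the cut-off.

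Elsewhere the two events are kept apart:

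- Protocol 3.6 deals with discontinuing the investigational product. Protocol 3.7.2 deals with leaving the study altogether: "Subjects are free to withdraw from the study at any time (investigational product and assessments".
- SAP 4.3.1 has separate disposition lines for completing treatment, completing the study and discontinuing the study early.
- Protocol 8.3 keeps operated subjects in the RP analysis set "regardless of prematurely discontinued treatment", and SAP 3.1 counts operated early stoppers in the primary endpoint.
- For operated subjects, Protocol 3.7.4 says that "it will be considered as completion of the study if the subjects completed the 3 months post-surgical follow-up period".
- Under the liver rule in Protocol 6.10, "Casodex should be immediately discontinued with close follow-up of liver function". That section does not say that the subject then leaves the study.

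**The concern.** A compliance rate should show how much of the prescribed drug a subject took while it was prescribed. Once a drug has been permanently stopped, none of it is prescribed. If the subject remains in the study and withdraws later, the special rule still adds the doses that would have fallen between the two dates. This departs from the prescribed-number denominator given in the same paragraph. It also departs from SAP 4.3.5.1, where Casodex exposure ends at the last tablet, so exposure and compliance would run to different end dates for one subject.

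Early discontinuation is then reported as poor adherence. Two subjects with the same dosing history get different rates only because one stayed in the study longer. For a stopper who goes on to complete the study, the programmer has to invent a cut-off.

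**Working it through.** The documents state no compliance figure, so there is none to reproduce. The check applies the SAP formula with two cut-offs.

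**Inputs from the documents**

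- Casodex: one tablet daily for 24 weeks (Protocol 7.2), so 24 × 7 = 168 tablets.
- Zoladex: two implants, at Day 1 and Day 85 (Protocol 4.1).
- Surgery within 30 days after end of treatment, last follow-up visit 90 days after surgery (Protocol 4.1).

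**Assumed for illustration:** the stop day *s*, the exit day *w*, and every dose taken up to *s*.

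**Formulas**

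- Casodex, SAP rule: 100 × *s* / min(*w*, 168) if expected tablets are capped at the planned course; 100 × *s* / *w* if not. SAP 3.4 states no cap.
- Zoladex, SAP rule: 100 × implants given / implants due by *w*.
- Counting to the permanent stop: 100 × *s* / *s* = 100%, whatever the exit day.

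**Subjects with a withdrawal date**

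| Case | SAP rule | Counted to stop |
|---|---|---|
| Casodex, stop Day 60, withdrawn Day 60 | 60/60 = 100% | 100% |
| Casodex, stop Day 60, withdrawn Day 88 | 60/88 = 68.2% | 100% |
| Casodex, stop Day 60, withdrawn Day 144 | 60/144 = 41.7% | 100% |
| Zoladex, one implant then stopped, exit before Day 85 | 1/1 = 100% | 100% |
| Zoladex, one implant then stopped, exit on or after Day 85 | 1/2 = 50% | 100% |

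The cap plays no part in the Casodex rows, because each exit falls before Day 168.

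**A stopper who completes the study**

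He has no withdrawal date, so the rule returns nothing. Suppose the completion date is put in its place. For a stop on Day 84, surgery 30 days later and 90 days of follow-up, *w* = 84 + 30 + 90 = 204. The result is 84/168 = 50% capped, or 84/204 = 41.2% uncapped.

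**Effect on the mean**

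Let a share *f* of subjects be such Day 84 stoppers, fully adherent until the stop and followed to Day 204, with everyone else at 100%. Mean Casodex compliance is 100 × [(1 − *f*) + *f* × *r*], where *r* is 0.50 capped or 0.412 uncapped. The correct mean is 100%.

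| *f* (assumed) | Capped | Uncapped |
|---|---|---|
| 5% | 97.5% | 97.1% |
| 10% | 95.0% | 94.1% |
| 20% | 90.0% | 88.2% |

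The documents give no rate of stopping drug while staying in the study. The 10% in SAP 1.3 is a dropout rate, which is a different quantity.

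**The case against.** The best defence is that the sentence is a slip: it opens with stopping study medication, so study withdrawal may have been meant as withdrawal of study medication. On that reading nothing is miscalculated. This is plausible, but the SAP nowhere says so, and as worded the instruction sets a different date.

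A second defence is that the rule only truncates the planned schedule. Casodex is scheduled to Week 24 and Zoladex at two visits, so nothing is expected after that and the 168-tablet cap is the natural reading. A reader might infer that the SAP counts every post-surgical day as a missed tablet, and might carry a Day 60 stopper to Day 169 + 30 + 90 = 289, for 60/289 = 21%. The documents do not support that reading. The denominator is expected doses, not calendar days, and with the cap the figure is 60/168 = 36%. Day 289 is itself doubtful. SAP 4.1 ends treatment 12 weeks after the last injection, which after one implant is about Day 85. Surgery would then be due by about Day 115 and follow-up would end by about Day 205. The cap reduces the error but does not remove it, as the Day 88 and Day 144 cases show.

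A third defence is that compliance with the whole planned course is a legitimate summary. It is, but that would use 168 tablets and two implants for everyone, and a cut-off at withdrawal does not do that.

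It is also true that little depends on this number. SAP 4.3.5.2 lists each subject's expected and actual counts, so the figures can be traced.

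**Conclusion.** The rule is wrong as written, and the matter is minor. It understates compliance when study withdrawal falls after drug stop, and it gives no cut-off for a stopper who completes the study.

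A reader might infer that the rate is wrong for every early stopper. It is not. When the two dates coincide the rules agree, and Zoladex is affected only when the Day 85 implant falls between stop and exit.

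In the cases worked with a withdrawal date, a fully adherent Casodex stopper reads 68% or 42% instead of 100%. A Day 84 stopper who completes reads 50% (41% uncapped), but only if the completion date is used for the missing withdrawal date. Mean compliance would fall by 2.5 to 10 percentage points with the cap, or about 3 to 12 without it, if 5% to 20% of subjects were such Day 84 stoppers. All of these rest on assumed dates, assumed rates and full adherence up to the stop.

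Only a descriptive summary on the full analysis set is affected. The primary endpoint, the analysis sets and the sample size do not use compliance.

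**What to change.** Replace the special rule in SAP 3.4 with:

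> For subjects who permanently stop Zoladex or Casodex, expected doses of that drug are counted from first dose to the date of its permanent discontinuation, and not beyond the planned 24-week course.

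Report early discontinuation of each drug on its own line in the disposition or exposure tables, so that it stays visible once it no longer lowers the compliance rate. This changes how doses are counted and no dosing or stopping rule. The cost is one SAP sentence, a table line and a small programming change, best made before database lock.
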